2. BACKGROUND AND RATIONALE

Stroke is one of the leading causes of adult disability. Current physical therapies for stroke are both limited in their success and are time demanding, with the latter factor increasing the cost of therapy. It has been reported that following stroke, many people experience issues with sleep, which has been shown to play an important role in consolidation of learning. Our current research confirms this, indicating that chronic community dwelling stroke survivors experience poorer sleep quality than age matched healthy controls.

“Sleepio” is an online Cognitive Behavioural Therapy for Insomnia (CBT-I) programme developed by researchers at the Sleep and Circadian Neuroscience Institute (SCNI), University of Oxford, to improve sleep quality. The programme takes the users through a six-week programme designed to educate the user on their sleep and to improve their sleep quality. The efficacy of this intervention has been demonstrated in people with chronic insomnia³ but has not yet been tested in people with stroke. We have recently conducted a mixed methods feasibility study to explore stroke survivors perceptions of using the programme, and this has indicated that with some additional information provided to participants, the programme is useable in its current form. Therefore, the present study will investigate the efficacy of digital CBT-I for chronic stroke survivors.

3. STUDY DESIGN

The study will be a single-blinded randomised controlled trial involving the completion of a six-week digital CBT-I programme. Following written informed consent, participants will be posted baseline questionnaires to complete and an actigraphy monitor to record objective sleep measures for one week. After this, participants will be randomised to CBT-I or control using an online randomisation software (rando.la) with minimisation of between group differences based on age and baseline self-reported sleep quality (Sleep Condition Indicator (SCI) score). The control group will be given access to an online sleep diary to complete daily for one week. They will also be given a brochure containing sleep hygiene information. 8 weeks later they will be asked to complete the online sleep diary again for one week.

Participants allocated to Sleepio will complete daily online sleep diaries for the duration of the study and will receive weekly online CBT-I sessions as part of the programme. Both groups will complete their programmes at home.

Participants will be sent the questionnaires and actigraphy monitor again to be worn for another week immediately following completion of the programme (Sleepio) or following the 6-week sleep diary (control) and at 8 weeks follow up. At 8 weeks follow up, participants in the intervention group will also be sent a debriefing questionnaire to get feedback on the programme and the research study.

Participants allocated to the control group will be sent a web link and activation code for the Sleepio programme following completion of the 8 week follow up.

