1. SYNOPSIS

Long Study Title	An Investigation into the Efficacy of Online Cognitive Behaviour Therapy for Insomnia (“Sleepio”) for Stroke Survivors	
Short Study Title (to be used on participant-facing documents, if applicable)	Improving sleep in rehabilitation after stroke (INSPIRES)	
Nature of Study Participants	Stroke survivors	
Intended number of participants	86	
Design	Randomised controlled	
Location	In the participant's home / online	
	Objectives	Outcome Measures
Primary	The primary objective of this study is to assess whether self-reported sleep quality in stroke survivors is improved following online Cognitive Behavioural Therapy for Insomnia (“Sleepio” programme).	The primary outcome measures for this study will be the change in Sleep Condition Indicator score following completion of the programme.
Secondary	
The secondary objectives are to assess changes in measures of sleep quality and self-reported measures of quality of life and anxiety following the intervention and at 8 week follow up.
 
To assess the cost-effectiveness of online CBT-I in stroke survivors when compared to a brochure of sleep hygiene information.
	
Changes in sleep fragmentation and wake after sleep onset, assessed with actigraphy, sleep onset latency assessed through the sleep diaries, anxiety and depression using the PHQ9 and GAD7, quality of life using the Stroke impact scale-8 and Euroqol-5 Dimensions- 5 Levels (EQ-5D-5L)
 
Changes in healthcare costs during the 8-week follow up.

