5.5. Baseline Assessments

After the signed consent form has been received by the researchers, the participant will be sent the GAD-7, PHQ-9, SCI, Stroke Impact Scale-8, Stroke Efficacy questionnaire and EQ-5D-5L to complete. Participants will also receive a questionnaire asking them to recall over the last 8 weeks all the contacts they have had with the healthcare service. This will be a modified version of the Client Service Receipt Inventory (CSRI).

We will also ask them to wear an actigraphy monitor on their wrist for one week and to complete a sleep diary at the same time. We will provide them with a prepaid envelope to send the materials back.

We will also record demographic variables including; age, sex, partner status, whether they share a bed, medications, employment status and date of stroke.

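### The primary SCI assessment is triggered by finishing the programme (Sleepio) or a six-week diary that the plan does not otherwise give to controls, with no date from randomisation, no window and no rule for non-completers

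*Combined protocol and SAP*

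**What the plan says.** The synopsis defines the primary outcome as the "change in Sleep Condition Indicator score following completion of the programme". It gives no week number and no counterpart for the control arm.

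Section 3 gives each arm its own trigger for the second set of questionnaires: "immediately following completion of the programme (Sleepio) or following the 6-week sleep diary (control) and at 8 weeks follow up". Section 5.6 names a single trigger for all participants, completion of the programme.

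On the control diary, section 3 says "The control group will be given access to an online sleep diary to complete daily for one week", and then "8 weeks later they will be asked to complete the online sleep diary again for one week". Section 5.6 describes the same two diary periods.

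The only duration attached to the intervention is its nominal length. Section 2 says: "The programme takes the users through a six-week programme designed to educate the user on their sleep". Section 3 also calls the programme six-week.

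For baseline, section 5.5 says "the participant will be sent the GAD-7, PHQ-9, SCI, Stroke Impact Scale-8, Stroke Efficacy questionnaire and EQ-5D-5L to complete". The corresponding list in section 5.6 for the post-programme pack has PHQ-9, GAD-7, SIS-8, the Stroke Efficacy questionnaire and EQ-5D-5L, but not the SCI. Section 5.6 then repeats every baseline assessment at the 8-week follow-up.

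Section 8.1 makes the primary comparison the SCI from baseline to immediately post-intervention, by intention to treat. It uses ANOVA with the baseline score as covariate, or a linear mixed model or non-parametric equivalent if necessary.

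**The concern.** An intention-to-treat comparison needs the outcome sought from everyone randomised, at a time that does not depend on what they did after randomisation. Here the written rule makes both whether and when the primary outcome is measured depend on adherence, and in one arm only. People who abandon a sleep programme are unlikely to be a random subset of those offered it. If they are not assessed, the Sleepio mean describes completers, while the control mean describes everyone who was sent a pack. If slow users are assessed late, elapsed time differs between arms as well as treatment.

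There is also a practical problem. The event that should prompt the control mailing is not defined anywhere, so staff must choose a date themselves.

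**Working it through.** The plan states no figure for the timing of the primary assessment, so there is none to reproduce. The check is a comparison of the text.

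**1. What triggers the post-intervention SCI?**

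| Source | Sleepio | Control |
|---|---|---|
| Synopsis | completing the programme | not stated |
| Section 3 | completing the programme | end of a six-week diary |
| Section 5.6 | completing the programme | same words, but controls get Sleepio only after follow-up |
| Section 8.1 | immediately post-intervention | immediately post-intervention |

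Section 3 does add "Both groups will complete their programmes at home", which treats the control condition as a programme too. It does not say when that programme ends.

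**2. Is there a six-week control diary?** Sections 3 and 5.6 schedule one week of online diary, then another 8 weeks later. Neither lasts six weeks. Reading the phrase as a diary kept at week 6 does not help, because no control online diary is scheduled then. The post-programme pack in section 5.6 does include a one-week diary, but that diary is part of the assessment and cannot be the event that prompts it.

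**3. Is there a date, window or non-completer rule?** None is given. Section 6.1 records reasons for withdrawal where known, and does not say when or whether such participants are assessed.

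**4. Is the SCI in the pack?** It is in the section 5.5 list and missing from the post-programme list in section 5.6. Section 3 says the questionnaires are sent again, so the omission is probably a slip. It does, however, concern the primary outcome at the primary time point.

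**5. What does a late finish do to the interval?** Inputs: a nominal six-week programme (sections 2 and 3), and about one week of baseline recording before randomisation (section 3). I assume that the baseline SCI is completed at the start of that week and that the programme starts at randomisation.
- Nominal baseline-to-outcome interval: 1 + 6 = 7 weeks.
- Each week of overrun: 1/7 = 14% longer than for a control assessed at week 6. Postal delay before randomisation would lengthen the base and lower this percentage.

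This is a ratio of durations, not an estimate of bias.

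**6. When is the 8-week follow-up?** The synopsis lists assessments "following the intervention and at 8 week follow up" and gives no origin. Counted from randomisation, follow-up is week 8. Counted from the nominal end of the programme, it is week 6 + 8 = 14. The documents settle neither.

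**The case against.** The strongest reply is that this is loose wording around an obvious intention. The programme is six weeks long with weekly sessions, the control label also says six weeks, and section 8.1 commits to intention to treat. On that reading everyone is assessed at about week 6. The SCI is also repeated at follow-up, and a mixed model could use it for participants who miss the earlier assessment. Much of this stands: a week-6 target is a fair inference, and the mitigation is real. But follow-up is not the primary time point, the mixed model is only a fallback, and the intended time is never tied to randomisation.

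A second reply is that completion could remain the trigger, with a latest date for everyone. That would close the gap for non-completers. It would still let timing vary with behaviour in one arm.

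Four stronger readings are tempting, and the documents do not support them:

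- *A reader might infer that non-completers will go unassessed.* No section says so. The wording leaves the risk open.
- *A reader might put each week of overrun at 17% (1/6).* That leaves out the baseline period before randomisation. On the assumptions in the working, the figure is at most about 14%.
- *A reader might infer that the sample size has no slack for such losses.* Recruiting 86 gives 43 per arm against 34 needed, a margin of 9 (9/43 = 21%), while 25% of 43 is about 11. That shortfall exists whatever triggers the assessment. Participants who stop Sleepio may already be counted in the 25%, and 34 is not a cliff: at d = 0.7 with a two-sided 5% t-test, power is 81.2% at 34 per arm and 78.7% at 32.
- *A reader might infer that the repeat control diary matches neither later assessment.* If the first diary starts at randomisation, the repeat starts at week 8 or 9. That is clear of both assessments only if follow-up is at week 14. If follow-up is at week 8, the two roughly coincide. A diary is in any case part of each assessment pack, and the SCI is a separate questionnaire.

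**Conclusion.** The concern holds as a defect in how the primary assessment is specified, and it should be fixed. The triggers differ by arm, the control trigger contradicts the plan's own diary schedule, the SCI is missing from the section 5.6 list, and no date from randomisation, window or non-completer rule is given. Followed as written, the rule conflicts with the intention-to-treat comparison in section 8.1.

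The size and direction of any bias cannot be computed, because the documents do not say how many Sleepio users will stop early or overrun, or how their SCI scores would differ. The conclusion rests on the literal wording. If staff in practice mail every participant at week 6, the harm largely disappears, but the protocol does not instruct them to.

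**What to change.** - Send the post-intervention pack to every randomised participant in both arms at one common time from randomisation, namely the nominal end of the six-week programme, with a stated window, whether or not the programme or diary was finished.
- Name the SCI in the section 5.6 list.
- Amend the primary outcome wording in the synopsis, and the triggers in sections 3 and 5.6, to match.
- Reconcile the three descriptions of the control diary: one week, six weeks, and a repeat 8 weeks later.
- State one origin for the 8-week follow-up, common to both arms.

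The cost is protocol wording and mailing dates. It does change the definition of the primary outcome, from a completion-based time to a fixed one, so it needs a formal amendment. The drawback is that some slow Sleepio users will be measured before their last session. How many cannot be told from the documents, and the stated window can limit it.

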5.6. Subsequent Assessments

Participants randomised to the intervention group will receive access, via web link and activation code to the digital CBT-I programme “Sleepio”. This programme will require the participant to keep a daily sleep diary and engage in weekly sessions comprising weekly CBT-I content. Participants randomised to the control group will be given access to an online sleep diary to complete for one week. They will also receive a brochure with sleep hygiene information and then will be asked to complete the online sleep diary again 8 weeks later.

During the trial, participants will be asked to keep a record, in a specially designed log book, of their contacts with the healthcare service.

Upon completion of the programme, participants will once again be sent questionnaires to complete (PHQ-9, GAD-7, SIS-8, Stroke Efficacy questionnaire and EQ-5D-5L), in addition to the wrist worn actigraphy monitor and the sleep diary to use for one week.

At 8 weeks follow up, all assessments conducted as baseline will be repeated and the intervention group will complete a debriefing feedback questionnaire.

6. Feasibility and Adverse events

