6.1. Feasibility of recruitment and adherence

We will record the number of people who express an interest in participating, the number who consent and the number who complete the study as an estimate of feasibility of recruitment to the study and completion of the CBT-I programme for this population.

Where known, we will record any reason for declining to take part or withdrawal from the study.

We will also send a debriefing questionnaire to participants at the end of the study to ask for their opinions of the study and the sleep improvement programme, and whether they had any CBT-I from other sources during the course of the study.

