8. STATISTICS AND ANALYSIS

8.1. Description of Statistical Methods

The efficacy of Sleepio will be assessed by comparing the SCI scores of the intervention and control groups from baseline to immediately post-intervention, following an intention to treat analysis approach. Changes in the primary outcome measure from baseline to post-intervention will be assessed with analysis of variance (ANOVA) (or linear mixed model or non-parametric equivalents if necessary) with inclusion of baseline score as a covariate.

Secondary outcomes will be assessed with ANOVA (or linear mixed model or non-parametric equivalents if necessary). EQ-5D-5L responses will be converted into utility values using population preferences (van Hout et al., 2012) and combined with survival information to calculate Quality Adjusted Life-Years (QALYs). All resource use will be valued using 2018/19 unit costs obtained from healthcare compendiums, (Curtis and Burns 2018) NHS reference costs, (<https://improvement.nhs.uk/resources/reference-costs/>) and British National Formulary (<https://www.bnf.org/>). Costs of CBT-I will be obtained from the trial.

An incremental analysis will be performed, assessing the differences in costs between the two interventions and dividing by the difference in QALYs gained in order to generate an incremental cost-effectiveness ratio (ICER). ICERs will be estimated using an NHS perspective. The 10 000 bootstrapped pairs of incremental costs and incremental QALYs will be plotted on cost-effectiveness planes to display the uncertainty in the estimated ICER. Cost-effectiveness acceptability curves (CEACs) will be derived to display the probability of the CBT treatment being cost-effective, as the ceiling ratio for the maximum acceptable cost-effectiveness ratio varies from £0 to £85 000 per QALY gained.

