8.2. The Number of Participants

68 full datasets (1:1 ratio intervention to control) are intended to be collected for this study. This is based on a power calculation using the between groups effect size estimate ($d=1.2$) from a previous study of digital CBT-I in people with insomnia (Espie et al., 2012). This would therefore require 24 participants in total to find an effect. However, we wish to also include people with sleep disturbance who do not meet the criteria for insomnia. Based on our open-label feasibility study for digital CBT-I in this population (Smejka et al., 2022) we anticipate that 50% of participants will not meet the criteria for insomnia, and based on that study we would anticipate a more modest effect size ($d=0.7$), which would require 68 participants (assuming $\alpha=0.05$ and power of 80%). Allowing for approximately 25% drop out, we therefore aim to recruit 86 participants in total. This should allow us to do a subgroup analysis including only people who meet the criteria for insomnia, as well as a full group analysis.

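### Hold the debriefing questionnaire until each participant's 8-week outcome materials are back: as written, the Sleepio arm may appraise its programme before or while rating those outcomes

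*Combined protocol and SAP*

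**What the plan says.** Three sections of the combined protocol and SAP describe the debriefing questionnaire.

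- Section 3 (Study Design) sends both arms the questionnaires and the actigraphy monitor after the programme and again at the 8-week follow-up. It then adds: "At 8 weeks follow up, participants in the intervention group will also be sent a debriefing questionnaire to get feedback on the programme". The sentence goes on to include feedback on the research study.
- Section 5.6 (Subsequent Assessments) says that at 8 weeks "all assessments conducted as baseline will be repeated and the intervention group will complete a debriefing feedback questionnaire". By section 5.5, the baseline assessments include the SCI, PHQ-9, GAD-7, SIS-8, EQ-5D-5L and a sleep diary.
- Section 6.1 (Feasibility of recruitment and adherence) says: "We will also send a debriefing questionnaire to participants at the end of the study to ask for their opinions of the study". It names no arm. It adds that the form covers views of the sleep programme and any CBT-I obtained elsewhere.

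On blinding, section 3 says: "The study will be a single-blinded randomised controlled trial involving the completion of a six-week digital CBT-I programme". It does not say who is blinded.

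On timing of the endpoints, section 8.1 bases the efficacy assessment on "comparing the SCI scores of the intervention and control groups from baseline to immediately post-intervention". The synopsis gives the secondary objectives as changes in sleep quality and in "self-reported measures of quality of life and anxiety following the intervention and at 8 week follow up".

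**The concern.** The 8-week measures are mostly self-reported, and participants complete them at home. One arm has followed a six-week online programme. The other has had a brochure and a sleep diary, with Sleepio promised after follow-up. Participants very likely know which arm they are in.

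In that setting, a form asking one arm for its opinion of its treatment is a cue that the other arm does not get. If it is opened before or during the outcome week, the answers on sleep, mood and quality of life may drift towards the opinion just given. Analysis could not separate such a drift from a treatment effect.

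At stake are the between-arm comparisons of self-reported secondary outcomes at 8 weeks, and the last EQ-5D-5L value entering the QALYs behind the ICER.

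**Working it through.** **Step 1. Sections side by side.**

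| Point | Section 3 | Section 5.6 | Section 6.1 |
|---|---|---|---|
| Recipients | Intervention group | Intervention group | Participants, no arm named |
| Timing | 8-week follow-up | 8-week follow-up, with the repeated assessments | End of study |
| Same mailing as outcome forms? | Not stated | Not stated | Not stated |
| Order relative to outcome forms | Not stated | Not stated | Not stated |

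Under sections 3 and 5.6 the form goes to one arm at the time of the outcome assessment. Nothing there stops it being completed first. Section 6.1 leaves the recipients open.

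**Step 2. Which results are exposed.** The primary comparison ends immediately after the intervention, before any debriefing, so it is not touched. (The post-programme list in section 5.6 does not name the SCI, but the synopsis and section 8.1 both place the primary SCI measurement at that point.) Actigraphy is not self-reported. That leaves the 8-week self-report outcomes.

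**Step 3. The plan's own sample size.** Section 8.2 states: "we would anticipate a more modest effect size ($d=0.7$), which would require 68 participants". A two-sample t-test (non-central t, two-sided α = 0.05, power 80%, 1:1) needs 33.02 per arm, rounded up to 34, so 2 × 34 = 68. The plan's figure is reproduced. Power with 34 per arm at d = 0.7 is 81%. Section 8.2 does not say whether α is two-sided, but a one-sided test would need only 52.

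**Step 4. Sensitivity of an 8-week comparison.** The documents give no size for a priming effect, so the shifts b below are assumptions. With no true effect, a shift of b SD in one arm gives non-centrality b × √(34/2). The two-sided rejection rate is then:

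| Assumed shift b (SD) | Non-centrality | Rejection rate |
|---|---|---|
| 0 | 0 | 5.0% |
| 0.05 | 0.206 | 5.5% |
| 0.1 | 0.412 | 6.9% |
| 0.2 | 0.825 | 12.8% |

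A shift in either direction gives the same rejection rate. For comparison, 0.2 SD is 0.2/0.7 = 29% of the planned effect, which is a lot to attribute to a feedback form.

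**Step 5. Sensitivity of the QALYs.** Further assumptions: EQ-5D-5L utility SD of 0.20 to 0.25; linear interpolation between assessments; 6 weeks from baseline to post-intervention and 8 weeks from there to follow-up. A shift in the last value alone changes the QALYs by 0.5 × b × SD × 8/52.

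- b = 0.1, SD = 0.20: 0.5 × 0.1 × 0.20 × 8/52 = 0.0015
- b = 0.2, SD = 0.25: 0.5 × 0.2 × 0.25 × 8/52 = 0.0038

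Reference, assuming a true utility gain of 0.05 at both later time points: 0.5 × 0.05 × 6/52 + 0.05 × 8/52 = 0.0029 + 0.0077 = 0.0106. The shifts are 15% to 36% of that, upwards or downwards.

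Steps 4 and 5 show only how sensitive the results would be if a shift occurred. They do not estimate the bias to expect.

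**The case against.** The case against is substantial, and most of it stands.

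- **Same pack.** A reader might infer that the form travels in the outcome pack or is filled in just before the outcomes. Sections 3 and 5.6 give the same time point but neither a shared mailing nor a sequence. If the form is completed last, which the text equally allows, the cue disappears. What remains is that the plan does not secure that order.
- **One arm only.** A reader might take it as settled that only the Sleepio arm is debriefed. Section 6.1 names no arm. If it governs, both arms are debriefed and the asymmetry shrinks or goes.
- **Conflict on timing.** A reader might see a contradiction between the 8-week follow-up and the end of the study. The 8-week visit is the last assessment described, and section 7 ends the study at the last participant's last follow-up response. For a given participant the two can coincide. The discrepancy that needs settling is who receives the form.
- **Content and direction.** The questionnaire is not in the documents. It is described as seeking opinions of the programme and the study, not a rating of efficacy. A critical response could lower later scores as readily as a favourable one could raise them.
- **Added effect.** Participants who very likely know their arm, and who have followed weekly sessions, may already respond with that knowledge in mind. Nothing in the documents shows that a feedback form adds a detectable amount.

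None of this gives a reason to leave the order open when closing it costs so little.

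**Conclusion.** This holds as a small, cheap improvement and not as a flaw in the trial's main inference. The plan permits the intervention group to appraise its programme before or while it rates its 8-week outcomes. The resulting bias is of unknown size and direction and is probably small. It is confined to the 8-week self-report secondary outcomes and the final EQ-5D-5L value.

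The conclusion rests on two readings: that sections 3 and 5.6 govern who receives the form, and that participants know their allocation. The second is very likely given the two interventions, although the single-blind statement does not name the blinded party.

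A reader might infer from the illustrative figures that 8-week false-positive rates will be inflated, or the QALY difference distorted, by those amounts. The documents do not support that, because every shift, SD and utility gain used is assumed.

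The unclear recipients matter for a second reason. The form also asks about CBT-I from other sources, so if only the Sleepio arm receives it, outside CBT-I in controls would not be captured by this form.

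**What to change.** In sections 3 and 5.6, state that the debriefing questionnaire is sent, by post, email or online, only after the participant's 8-week questionnaires, sleep diary and actigraphy monitor have been returned. In the same edit, reconcile the recipients with section 6.1. Either name the intervention group there, or say in sections 3 and 5.6 that both arms are debriefed and which items go to each. The order works whichever recipients are chosen.

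The cost is a sentence in each of two sections, a matching edit on recipients, and one later mailing or email. That is at most about 86/2 = 43 participants if only the intervention arm is debriefed, or up to 86 if both are. A few debriefing forms may not come back, which would slightly thin the feasibility feedback but not the efficacy data. Sample size, endpoints and analysis do not change.
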